9.0 ADVERSE EVENTS

9.1 Adverse Event (AE) Monitoring

The investigator or qualified designee will assess each subject to evaluate for potential new or worsening AEs as specified in the Schedule of Events and more frequently if clinically indicated. Adverse experiences will be graded and recorded throughout the study and during the follow-up period according to NCI CTCAE Version 4.0. Toxicities will be attributed and graded, and action taken with regard to trial treatment will be recorded.

AEs will be attributed as unrelated, related or possibly related to:

- 1) pembrolizumab
- 2) ferumoxytol
- 3) standard of care stereotactic radiosurgery

For subjects receiving treatment with pembrolizumab, all AEs of unknown etiology associated with Pembrolizumab exposure should be evaluated to determine if it is possibly an event of clinical interest (ECI) of a potentially immunologic etiology (termed immune-related adverse events, or irAEs).

9.2 Sponsor Responsibility for Reporting Adverse Events

All Adverse Events will be reported to regulatory authorities, IRB/IECs and investigators in accordance with all applicable global laws and regulations.

9.3 OHSU IRB Reporting of Unanticipated Problems and Adverse Events

Unanticipated Problems (UP) and Adverse Events (AE) will be reported to OHSU IRB according to the policies, procedures and guidelines posted on the OHSU IRB web site <http://www.ohsu.edu/research/rda/irb/policies.shtml>.

Fatal and life-threatening events must be reported to OHSU IRB within 5 working days after the PI learns of the event. If any of these require a change (as determined by the PI or the IRB) to the protocol or consent form, the PI will make those changes promptly and submit the revised documents to the OHSU IRB.

All other UP reports will be submitted to OHSU IRB no later than 15 calendar days of notification of the event. If the event requires changes as determined by the PI or the IRB) to the protocol or consent form, the PI will make the changes promptly and submit the revised

documents to the IRB. UP and AE reports are submitted through OHSU e-IRB and will be reviewed by OHSU IRB.

9.4 Assessing and Recording Adverse Events

An adverse event is defined as any untoward medical occurrence in a patient or clinical investigation subject administered a pharmaceutical product and which does not necessarily have to have a causal relationship with this treatment. An adverse event can therefore be any unfavorable and unintended sign (including an abnormal laboratory finding, for example), symptom, or disease temporally associated with the use of a medicinal product or protocol-specified procedure, whether or not considered related to the medicinal product or protocol-specified procedure. Any worsening (i.e., any clinically significant adverse change in frequency and/or intensity) of a preexisting condition that is temporally associated with the use of the Merck's product, is also an adverse event.

Changes resulting from normal growth and development that do not vary significantly in frequency or severity from expected levels are not to be considered adverse events. Examples of this may include, but are not limited to, teething, typical crying in infants and children and onset of menses or menopause occurring at a physiologically appropriate time.

Merck product includes any pharmaceutical product, biological product, device, diagnostic agent or protocol-specified procedure, whether investigational (including placebo or active comparator medication) or marketed, manufactured by, licensed by, provided by or distributed by Merck for human use.

Adverse events may occur during the course of the use of Merck product in clinical trials or within the follow-up period specified by the protocol, or prescribed in clinical practice, from overdose (whether accidental or intentional), from abuse and from withdrawal.

Adverse events may also occur in screened subjects during any pre-allocation baseline period as a result of a protocol-specified intervention, including washout or discontinuation of usual therapy, diet, placebo treatment or a procedure.

Progression of the cancer under study is not considered an adverse event unless it is considered to be drug related by the investigator.

All adverse events will be recorded from the time the consent form is signed through 30 days following cessation of treatment and at each examination on the Adverse Event case report forms/worksheets. The reporting timeframe for adverse events meeting any serious criteria is described in Section 9.6.3.1.

9.5 Rescue Medications & Supportive Care

9.5.1 Supportive Care Guidelines

Subjects should receive appropriate supportive care measures as deemed necessary by the treating investigator. Suggested supportive care measures for the management of adverse events with potential immunologic etiology are outlined below. Where appropriate, these guidelines include the use of oral or intravenous treatment with corticosteroids as well as additional anti-inflammatory agents if symptoms do not improve with administration of corticosteroids. Note that several courses of steroid tapering may be necessary as symptoms

may worsen when the steroid dose is decreased. For each disorder, attempts should be made to rule out other causes such as metastatic disease or bacterial or viral infection, which might require additional supportive care. The treatment guidelines are intended to be applied when the investigator determines the events to be related to pembrolizumab.

Note: if after the evaluation the event is determined not to be related, the investigator is instructed to follow the ECI reporting guidance but does not need to follow the treatment guidance.. Refer to Section 7.5 for dose modification.

It may be necessary to perform conditional procedures such as bronchoscopy, endoscopy, or skin photography as part of evaluation of the event.

9.5.2 Expected AEs due to Pembrolizumab and Guidelines for Management

- **Pneumonitis:**

- For **Grade 2 events**, treat with systemic corticosteroids. When symptoms improve to Grade 1 or less, steroid taper should be started and continued over no less than 4 weeks.
- For **Grade 3-4 events**, immediately treat with intravenous steroids. Administer additional anti-inflammatory measures, as needed.
- Add prophylactic antibiotics for opportunistic infections in the case of prolonged steroid administration.

- **Diarrhea/Colitis:**

Subjects should be carefully monitored for signs and symptoms of enterocolitis (such as diarrhea, abdominal pain, blood or mucus in stool, with or without fever) and of bowel perforation (such as peritoneal signs and ileus).

- All subjects who experience diarrhea/colitis should be advised to drink liberal quantities of clear fluids. If sufficient oral fluid intake is not feasible, fluid and electrolytes should be substituted via IV infusion. For Grade 2 or higher diarrhea, consider GI consultation and endoscopy to confirm or rule out colitis.
- For **Grade 2 diarrhea/colitis** that persists greater than 3 days, administer oral corticosteroids.
- For **Grade 3 or 4 diarrhea/colitis** that persists > 1 week, treat with intravenous steroids followed by high dose oral steroids.
- When symptoms improve to Grade 1 or less, steroid taper should be started and continued over no less than 4 weeks.

- **Type 1 diabetes mellitus (if new onset, including diabetic ketoacidosis [DKA]) or \geq Grade 3 Hyperglycemia, if associated with ketosis (ketonuria) or metabolic acidosis (DKA)**

- For **T1DM or Grade 3-4 Hyperglycemia**
 - Insulin replacement therapy is recommended for Type I diabetes mellitus and for Grade 3-4 hyperglycemia associated with metabolic acidosis or ketonuria.

- Evaluate subjects with serum glucose and a metabolic panel, urine ketones, glycosylated hemoglobin, and C-peptide.
- **Hypophysitis:**
 - For **Grade 2** events, treat with corticosteroids. When symptoms improve to Grade 1 or less, steroid taper should be started and continued over no less than 4 weeks. Replacement of appropriate hormones may be required as the steroid dose is tapered.
 - For **Grade 3-4** events, treat with an initial dose of IV corticosteroids followed by oral corticosteroids. When symptoms improve to Grade 1 or less, steroid taper should be started and continued over no less than 4 weeks. Replacement of appropriate hormones may be required as the steroid dose is tapered.
- **Hyperthyroidism or Hypothyroidism:**

Thyroid disorders can occur at any time during treatment. Monitor subjects for changes in thyroid function (labs every 3 months) and for clinical signs and symptoms of thyroid disorders.

 - **Grade 2** hyperthyroidism events (and **Grade 2-4** hypothyroidism):
 - In hyperthyroidism, non-selective beta-blockers (e.g. propranolol) are suggested as initial therapy.
 - In hypothyroidism, thyroid hormone replacement therapy, with levothyroxine or liothyronine, is indicated per standard of care.
 - **Grade 3-4** hyperthyroidism
 - Treat with an initial dose of IV corticosteroid followed by oral corticosteroids. When symptoms improve to Grade 1 or less, steroid taper should be started and continued over no less than 4 weeks. Replacement of appropriate hormones may be required as the steroid dose is tapered.
- **Hepatic:**
 - For **Grade 2** events, monitor liver function tests more frequently until returned to baseline values (consider weekly).
 - Treat with IV or oral corticosteroids
 - For **Grade 3-4** events, treat with intravenous corticosteroids for 24 to 48 hours.
 - When symptoms improve to Grade 1 or less, a steroid taper should be started and continued over no less than 4 weeks.
- **Renal Failure or Nephritis:**
 - For **Grade 2** events, treat with corticosteroids.
 - For **Grade 3-4** events, treat with systemic corticosteroids.
 - When symptoms improve to Grade 1 or less, steroid taper should be started and continued over no less than 4 weeks.
- **Stevens-Johnson Syndrome (SJS) and Toxic Epidermal Necrolysis (TEN):**
 - One fatal case of SJS in a clinical trial and one fatal case of TEN in the post-marketing setting have been reported in patients treated with pembrolizumab.

Including these cases, there have been 8 cases of SJS (6 in clinical trials, and 2 post-marketing) and 2 cases of TEN (both post-marketing) all of which were serious.

- The risk of SJS and TEN is reported at approximately 0.4 - 7 cases per million patient years in the general adult population.
- Independent risk factors include certain medications such as anticonvulsants, sulfonamides, aminopenicillins, allopurinol, and NSAIDs. Non-medication triggers include infection, contrast media, and vaccinations.
- Maligancy is associated with an increased mortality rate in patients with SJS and TEN.

For signs or symptoms of SJS or TEN, withhold Pembrolizumab and refer the patient for specialized care for assessment and treatment. If SJS or TEN is confirmed, permanently discontinue Pembrolizumab.

- **Immune-mediated myocarditis**

A total of 6 cases of myocarditis have been reported in patients treated with pembrolizumab in clinical trials or in an expanded access program. There were 1 fatal case reported in a clinical trial.

A search of the literature identified neither background incidence rates nor prevalence of myocarditis specifically among cancer patients. Immune-mediated myocarditis should be suspected if other causes of myocarditis, such as infection or prior radiation therapy, have been excluded. Risk factors include certain medications and treatment modalities such as radiation, anthracycline, alkylating agents and most recently checkpoint inhibitors. For suspected immune-mediated myocarditis, ensure adequate evaluation to exclude other etiologies, and administer corticosteroids.

- **Management of Infusion Reactions:** Signs and symptoms usually develop during or shortly after drug infusion and generally resolve completely within 24 hours of completion of infusion.

Table 8 below shows treatment guidelines for subjects who experience an infusion reaction associated with administration of pembrolizumab (MK-3475).

Table 8 Infusion Reaction Treatment Guidelines

NCI CTCAE Grade	Treatment	Premedication at subsequent dosing
Grade 1 Mild reaction; infusion interruption not indicated; intervention not indicated	Increase monitoring of vital signs as medically indicated until the subject is deemed medically stable in the opinion of the investigator.	None
Grade 2 Requires infusion interruption but responds promptly to symptomatic treatment (e.g., antihistamines, NSAIDs, narcotics, IV fluids);	Stop Infusion and monitor symptoms. Additional appropriate medical therapy may include but is not limited to: IV fluids Antihistamines NSAIDS	Subject may be premedicated 1.5h (± 30 minutes) prior to infusion of Pembrolizumab (MK-3475) with: Diphenhydramine 50 mg po (or equivalent dose of antihistamine).

NCI CTCAE Grade	Treatment	Premedication at subsequent dosing
prophylactic medications indicated for <=24 hrs	
Acetaminophen Narcotics
 
Increase monitoring of vital signs as medically indicated until the subject is deemed medically stable in the opinion of the investigator.
 
If symptoms resolve within one hour of stopping drug infusion, the infusion may be restarted at 50% of the original infusion rate (e.g., from 100 mL/hr to 50 mL/hr). Otherwise dosing will be held until symptoms resolve and the subject should be premedicated for the next scheduled dose.
 
Subjects who develop Grade 2 toxicity despite adequate premedication should be permanently discontinued from further trial treatment administration.
	Acetaminophen 500-1000 mg po (or equivalent dose of antipyretic).

Grades 3 or 4
 
Grade 3: Prolonged (i.e., not rapidly responsive to symptomatic medication and/or brief interruption of infusion); recurrence of symptoms following initial improvement; hospitalization indicated for other clinical sequelae (e.g., renal impairment, pulmonary infiltrates)
 
Grade 4: Life-threatening; pressor or ventilatory support indicated
	
Stop Infusion.
 
Additional appropriate medical therapy may include but is not limited to:
 
 IV fluids Antihistamines NSAIDS Acetaminophen Narcotics Oxygen Pressors Corticosteroids Epinephrine 
Increase monitoring of vital signs as medically indicated until the subject is deemed medically stable in the opinion of the investigator.
 
Hospitalization may be indicated.
 
Subject is permanently discontinued from further trial treatment administration.
	No subsequent dosing
Appropriate resuscitation equipment should be available in the room and a physician readily available during the period of drug administration.		

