Diarrhea / Colitis	Grade 2 or 3	Withhold	
 Administer corticosteroids (initial dose of 1-2 mg/kg prednisone or equivalent) followed by taper 	
 Monitor participants for signs and symptoms of enterocolitis (ie, diarrhea, abdominal pain, blood or mucus in stool with or without fever) and of bowel perforation (ie, peritoneal signs and ileus). Participants with \geq Grade 2 diarrhea suspecting colitis should consider GI consultation and performing endoscopy to rule out colitis. Participants with diarrhea/colitis should be advised to drink liberal quantities of clear fluids. If sufficient oral fluid intake is not feasible, fluid and electrolytes should be substituted via IV infusion.
	Grade 4	Permanently discontinue		
AST/ALT elevation or Increased bilirubin	Grade 2	Withhold	
 Administer corticosteroids (initial dose of 0.5- 1 mg/kg prednisone or equivalent) followed by taper 	
 Monitor with liver function tests (consider weekly or more frequently until liver enzyme value returned to baseline or is stable)
	Grade 3 or 4	Permanently discontinue	
 Administer corticosteroids (initial dose of 1-2 mg/kg prednisone or equivalent) followed by taper 	

Type 1 diabetes mellitus (T1DM) or Hyperglycemia	Newly onset T1DM or Grade 3 or 4 hyperglycemia associated with evidence of β -cell failure	Withhold	
 Initiate insulin replacement therapy for participants with T1DM Administer anti-hyperglycemic in participants with hyperglycemia 	
 Monitor participants for hyperglycemia or other signs and symptoms of diabetes.
Hypophysitis	Grade 2	Withhold	
 Administer corticosteroids and initiate hormonal replacements as clinically indicated. 	
 Monitor for signs and symptoms of hypophysitis (including hypopituitarism and adrenal insufficiency)
	Grade 3 or 4	Withhold or permanently discontinue ¹		
Hyperthyroidism	Grade 2	Continue	
 Treat with non-selective beta-blockers (eg, propranolol) or thionamides as appropriate 	
 Monitor for signs and symptoms of thyroid disorders.
	Grade 3 or 4	Withhold or permanently discontinue ¹		

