Hypothyroidism	Grade 2-4	Continue	
 Initiate thyroid replacement hormones (eg, levothyroxine or liothyronine) per standard of care 	
 Monitor for signs and symptoms of thyroid disorders.
Nephritis and Renal dysfunction	Grade 2	Withhold	
 Administer corticosteroids (prednisone 1-2 mg/kg or equivalent) followed by taper. 	
 Monitor changes of renal function
	Grade 3 or 4	Permanently discontinue		
Myocarditis	Grade 1 or 2	Withhold	
 Based on severity of AE administer corticosteroids 	
 Ensure adequate evaluation to confirm etiology and/or exclude other causes
	Grade 3 or 4	Permanently discontinue		
All other immune-related AEs	Intolerable/persistent Grade 2	Withhold	
 Based on type and severity of AE administer corticosteroids 	
 Ensure adequate evaluation to confirm etiology and/or exclude other causes
	Grade 3	Withhold or discontinue based on the type of event. Events that require discontinuation include and not limited to: Guillain-Barre Syndrome, encephalitis		
	Grade 4 or recurrent Grade 3	Permanently discontinue		

1. Withhold or permanently discontinue pembrolizumab is at the discretion of the investigator or treating physician.

NOTE:

For participants with Grade 3 or 4 immune-related endocrinopathy where withhold of pembrolizumab is required, pembrolizumab may be resumed when AE resolves to \leq Grade 2 and is controlled with hormonal replacement therapy or achieved metabolic control (in case of T1DM).

Dosing interruptions are permitted in the case of medical/surgical events or logistical reasons not related to study therapy (e.g., elective surgery, unrelated medical events, subject vacation,

and/or holidays), not to exceed two cycles. Subjects should be placed back on study therapy within 3 weeks of the scheduled interruption in all cases other than when pembrolizumab is stopped for craniotomy to confirm progression or unless otherwise discussed with the Sponsor. The reason for interruption should be documented in the subject's study record.

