9.6 Additional IND Reporting Requirements for Ferumoxytol and Pembrolizumab

Sponsor-investigator of this IND is responsible for compliance with the FDCA (21 U.S.C. §§ 301 et. seq.) as well as the implementing regulations [Title 21 of the Code of Federal Regulations (CFR)]. Responsibilities include:

- Reporting any unexpected fatal or life-threatening suspected adverse reactions to this Division no later than 7 calendar days after initial receipt of the information [21 CFR 312.32(c)(2)]. If IND is in eCTD format, submit 7-day reports electronically in eCTD format. If IND is not in eCTD format, submit 7-day reports by telephone or fax;
- Reporting any (1) serious, unexpected suspected adverse reactions, (2) findings from other clinical, animal, or in-vitro studies that suggest significant human risk, and (3) a clinically important increase in the rate of a serious suspected adverse reaction to this Division and to all investigators no later than 15 calendar days after determining that the information qualifies for reporting [21 CFR 312.32(c)(1)]. If IND is in eCTD format, submit 15- day reports to FDA electronically in eCTD format. If IND is not in eCTD format, submit 15-day reports in paper format; and
- Submitting annual progress reports within 60 days of the anniversary of the date that the IND went into effect (the date clinical studies were permitted to begin) [21 CFR 312.33].

Table 9 Evaluating Adverse Events

An investigator who is a qualified physician, will evaluate all adverse events as to:

V4.0 CTCAE Grading	Grade 1	Mild; asymptomatic or mild symptoms; clinical or diagnostic observations only; intervention not indicated.
	Grade 2	Moderate; minimal, local or noninvasive intervention indicated; limiting age-appropriate instrumental ADL.
	Grade 3	Severe or medically significant but not immediately life-threatening; hospitalization or prolongation of hospitalization indicated; disabling; limiting self-care ADL.
	Grade 4	Life threatening consequences; urgent intervention indicated.
	Grade 5	Death related to AE
Seriousness	A serious adverse event is any adverse event occurring at any dose or during any use of Merck product that:	
	† Results in death; or	
	† Is life threatening; or places the subject, in the view of the investigator, at immediate risk of death from the event as it occurred (Note: This does not include an adverse event that, had it occurred in a more severe form, might have caused death.); or	

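### Section 9.5.2 ties steroids for Grade 3 or 4 pembrolizumab-related diarrhea/colitis to more than a week's persistence, in conflict with Table 6 and out of order with its own Grade 2 trigger

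*Combined protocol and SAP*

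**What the plan says.** Two places in the protocol advise on steroids for pembrolizumab-related diarrhea or colitis.

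- **Section 9.5.2, Diarrhea/Colitis entry.** At Grade 2, for an event "that persists greater than 3 days, administer oral corticosteroids". At Grade 3 or 4, for an event "that persists > 1 week, treat with intravenous steroids followed by high dose oral steroids". The same entry tells the site to watch for signs of bowel perforation.
- **Section 7.5, Table 6.** The colitis row withholds pembrolizumab at Grade 2 or 3 and stops it permanently at Grade 4. On the Grade 2 or 3 line, the steroid column reads "Administer corticosteroids (initial dose of 1-2 mg/kg prednisone or equivalent) followed by taper". The general instructions above the table add that, for severe and life-threatening immune-related events, the intravenous steroid comes first and the oral steroid follows. Neither the row nor the general instruction mentions persistence. The table's title covers toxicity management as well as dose modification.

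Section 9.5.1 introduces the Section 9.5.2 measures as suggestions, to be applied when the investigator judges the event related to pembrolizumab. It refers the reader to Section 7.5 for dose modification only. Section 7.9 leaves the final decision on supportive therapy to the investigator or primary physician.

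**The concern.** The two sections address the same decision for the same event. On day 2 of a related Grade 3 colitis, Table 6 advises steroids, while the condition in Section 9.5.2 is not met for several more days. A clinician who turns to Section 9.5.2 alone, the section headed as guidance for managing expected events, finds no steroid instruction for severe colitis in its first week.

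The order of the two triggers inside Section 9.5.2 also looks wrong: the milder event reaches its steroid instruction sooner than the severe or life-threatening one. What is at stake is clear safety guidance for a serious, recognised toxicity of the study drug. Nothing in the imaging analysis depends on it.

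**Working it through.** No statistical calculation applies. The check sets the texts side by side.

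**Step 1. Triggers by grade**

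| Grade | Section 9.5.2 | Table 6, colitis row | Table 6, general instructions |
|---|---|---|---|
| 2 | more than 3 days | steroids, no persistence condition | not addressed to this grade |
| 3 | more than 1 week | steroids, no persistence condition | IV first, no wait stated |
| 4 | more than 1 week | permanent discontinuation; no separate steroid entry legible on this line | IV first, no wait stated |

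The last column applies to Grades 3 and 4 because Table 9 in Section 9.6 describes Grade 3 as severe and Grade 4 as life-threatening. At Grade 4 the comparison rests on that general instruction, not on the colitis row.

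**Step 2. Length of the disagreement.** At Grade 3, Table 6 has no persistence condition and Section 9.5.2 has one of more than 7 days. The advice can therefore differ for up to 7 days.

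**Step 3. Order within Section 9.5.2.** 7 − 3 = 4 days. After day 3 and through day 7, a Grade 2 event meets its steroid condition and a Grade 3 or 4 event does not. This does not depend on Table 6.

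**Step 4. Fit with the grade definition.** Table 9 defines Grade 4 as "Life threatening consequences; urgent intervention indicated". A trigger of more than a week does not fit that definition.

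**Step 5. Other entries in Section 9.5.2.** Steroid instructions counted by event and grade: pneumonitis 2, colitis 2, hypophysitis 2, hyperthyroidism 1, hepatic 2, renal 2, myocarditis 1. The sum is 2 + 2 + 2 + 1 + 2 + 2 + 1 = 12, leaving out the infusion-reaction table. Only the 2 for colitis depend on duration. For comparison:
- Grade 3–4 pneumonitis: "immediately treat with intravenous steroids".
- Grade 3–4 hepatic events: "treat with intravenous corticosteroids for 24 to 48 hours".
- Suspected myocarditis: "ensure adequate evaluation to exclude other etiologies, and administer corticosteroids".

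**Step 6. Is there a tie-breaker?** Section 9.5.1 points to Section 7.5 for dosing only. The end of Section 7.5 invokes manufacturer guidelines for refractory or persistent effects once steroids have been started. Section 7.2 invokes them for dose reductions and discontinuations. None of these settles when steroids begin.

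**The case against.** The strongest case on the other side has four parts.

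**The guidance is advisory.** Section 9.5.1 calls the measures suggested, and Section 7.9 gives the physician the last word. This stands and lowers the weight of the point. It settles who decides, but not which written trigger is the guidance.

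**Section 9.5.2 does not forbid earlier steroids.** This also stands. A reader might infer that steroids are allowed only after a week, but the text contains no such restriction. Nor does the protocol as a whole leave severe colitis without a steroid instruction: the general instructions of Table 6 supply one, and pembrolizumab is already withheld or stopped. Those same instructions are what the one-week condition conflicts with.

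**At Grade 2 the texts can be read together.** A reader might infer an equal contradiction there. The documents do not support it. Table 6 gives a dose and taper at Grade 2 but no start time. Three days fits the work-up in Sections 9.5.1 and 9.5.2: exclude infection, and consider GI consultation and endoscopy. Some might point to the Table 6 row for other immune-related events, keyed to "Intolerable/persistent Grade 2", as showing that the table writes persistence where it is meant. That phrase defines which Grade 2 events enter the row and lead to withholding; it is not a rule for starting steroids. Deleting the three-day condition would also be a clinical trade-off, since Section 4.7 warns that steroids may dampen the immune response.

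**A wait allows other causes to be excluded.** This does not rescue the Grade 3 or 4 trigger. The guidance applies to events already judged related, and a diagnostic wait does not explain a longer trigger for the more severe event.

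**Conclusion.** The point holds at Grade 3 and 4. The one-week condition conflicts with the Table 6 colitis row at Grade 3 and with the Table 6 general instructions at Grades 3 and 4. It is 4 days longer than the Grade 2 trigger in the same entry, and it does not fit the protocol's own Grade 4 definition. The two sections can give different advice for up to 7 days at Grade 3, and nothing in the protocol ranks them.

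The conclusion assumes that an instruction with no persistence condition applies once the event is graded and judged related. Table 6 states no explicit clock. The inverted order within Section 9.5.2 does not need that assumption.

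This is a safety-wording defect worth correcting at the next amendment. A reader might infer harm to the trial's results, but no effect on endpoints, imaging data or sample size follows from the documents, and the number of subjects who would meet the conflict cannot be derived.

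**What to change.** 1. In the Diarrhea/Colitis entry of Section 9.5.2, delete the persistence clause (the words before the comma in "that persists > 1 week, treat with intravenous steroids followed by high dose oral steroids") from the Grade 3 or 4 bullet. The intravenous-then-oral sequence stays, and so does the requirement in Section 9.5.1 to look for other causes and judge relatedness.
2. Add one sentence saying that Table 6 governs if the two sections differ at Grade 3 or 4.
3. Leave the Grade 2 three-day condition to the sponsor's clinical judgment. Either keep it, as the timing for the Table 6 Grade 2 dose, or remove it, and say which.

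The cost is one deleted phrase and a sentence or two in an amendment, plus a memo to the study team. No patients, visits or procedures are added. Some subjects with Grade 3 or 4 colitis may receive steroids sooner. Section 4.7 already plans a separate analysis by steroid dose, so no new analysis is needed.
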